## 8 Quality Assurance and Control

### 8.1 Data Handling and record keeping/ archiving

Study data is recorded both with paper and with electronic Case Report Forms (p/eCRF). For each enrolled study participant a CRF is maintained. All CRFs are kept current to reflect the subject's status at each phase during the course of study. Participants cannot be identified in the CRF by name or initials and birth date but an appropriate coded identification is used. All study team members are authorized for the CRF entries and it is assured that any authorized person can be identified both for pCRFs and eCRFs. If pCRFs are used, the investigator's acronym as well as the subject ID is filled in and data are entered into an electronic file for analysis by the respective investigator and data get monitored by the assigned monitor. In case of a self-evident corrections, either the subject does it by himself or the investigator undertakes the correction by crossing out the word/sentence with a single horizontal line and by adding the correction including his personal identifier and the date.

SRF-371

Confidential and proprietary.

This document and its contents are confidential and proprietary to Sonova and shall not be reproduced or otherwise disclosed to anyone other than Sonova employees without written authorization from Sonova.

This printout is an uncontrolled copy. The original is stored in the Document Management System  
Template: TPL-368 [2]

Page 18/26

## Clinical Investigation Plan (CIP)

### 8.1.1 Specifications of source documents

Timing measures will be recorded for both procedures and any additional attempts. Data from questionnaires will be compiled, but not statistically analyzed. Other data includes source intake form and Noah packages containing tympanometry and reflex thresholds, RECD, and REUR data.

### 8.1.2 Record keeping/ archiving

All paper data will be stored in a locked filing cabinet at the Phonak Audiology Research Center (PARC). All electronic data files will be encrypted and stored on secure research computers. All identifying data will be stored at PARC. De-identified data will be shared with production to cross-check the quality of scans/ impressions, and with partners at Sonova Switzerland.

## 8.2 Data management

### 8.2.1 Procedures data review, database cleaning, queries

During data collection of the investigation, physical copies of the data will be compiled and digitized by the study manager on a daily basis. Data will be reviewed for mis-entries or inaccuracies as each data set is entered.

The extent and nature of monitoring appropriate for the clinical investigation including the strategy for source data verification (SDV) are based on considerations such as the objective, design, complexity, size critical data points and endpoints of the clinical investigation. A detailed plan for monitoring arrangements is provided separately from this CIP (TPL-160).

### 8.2.2 Procedures for verification, validation and securing of EDC system

Not applicable for this investigation.

### 8.2.3 Procedures to maintain and protect participant privacy.

The identifiable data kept at PARC will be destroyed as soon as the final analyses have been completed. The de-identified data will be kept for seven years after the publication of results. When the data are destroyed, paper records will be shredded by services provided at PARC. Electronic data will be encrypted as de-identified NOAH packages, where applicable, to be shared with Sonova Switzerland.

### 8.2.4 Procedures for data retention.

Digital records of anonymized data will be stored on company network drive.

### 8.2.5 Specified retention period.

Digital records will be archived for 7 years from date of acquisition.

### 8.2.6 Other aspects of clinical quality assurance, as appropriate.

Refer to LoESD for licensure, insurance status, and appropriate qualifications of researchers.

## 9 Amendments to the CIP

Amendments to the CIP, if necessary, will be updated with justification in this document.

## 10 Deviations from clinical investigation plan

Deviations from the CIP to protect the rights, safety and well-being of human participants under emergency circumstances may proceed without prior approval of the sponsor and the EC

SRF-371

Confidential and proprietary.

This document and its contents are confidential and proprietary to Sonova and shall not be reproduced or otherwise disclosed to anyone other than Sonova employees without written authorization from Sonova.

This printout is an uncontrolled copy. The original is stored in the Document Management System  
Template: TPL-368 [2]

Page 19/26

## Clinical Investigation Plan (CIP)

– such deviations will be documented and reported to the sponsor representative (Investigation Manager) and the EC as soon as possible. Apart from that the investigator is not allowed to deviate from this CIP unless that deviation does not influence the investigation data.

### 10.1 Procedures for recording, reporting and analyzing CIP deviations

Each deviation from the CIP will be documented including date of protocol deviation, name of investigator, participant ID, affected visit (if applicable), reason for deviation and anticipated influence on investigation data.

### 10.2 Notification requirements and time frames

Each deviation needs to be reported to the Sponsor (= Study Manager) and depending on the severity, also to the IRB

For locations under WCG IRB approval (Canada/US): For protocol deviations, reporting to WCG IRBs (including WIRB) is **required only** for deviations that harmed a subject or placed subject at risk of harm or a deviation made without prior IRB approval to eliminate an immediate hazard to a subject **within 5 days**.

(Source: [WCG IRB Investigator Guidance: Prompt Reporting Requirements \(HRP-071\)](#))

### 10.3 Corrective and preventive actions and principal investigator disqualification criteria

The Sponsor may disqualify a clinical investigator if the clinical investigator has repeatedly or deliberately failed to comply with applicable regulatory requirements or the clinical investigator has repeatedly or deliberately submitted false information to the sponsor or, if applicable, to the Ethics Review Board or Competent Authority, in any required report.

## 11 Device accountability

### 11.1 Accountability for investigational device

The PI or authorized designee keep records documenting the following in a written process:

- Names of participants who received, used, returned, or disposed of device
- Date of receipt, identification, and quantity of each investigational device (batch/serial number or unique code)
- Expiry date (if applicable)
- Date(s) of use
- Participant identification

### 11.2 Return of investigational device

The PI or authorized designee keep records documenting the following in a written process:

- Date on which the device was returned (if applicable)
- Date of return of unused, expired, or malfunctioning investigational devices (if applicable)

SRF-371

Confidential and proprietary.

This document and its contents are confidential and proprietary to Sonova and shall not be reproduced or otherwise disclosed to anyone other than Sonova employees without written authorization from Sonova.

This printout is an uncontrolled copy. The original is stored in the Document Management System

Template: TPL-368 [2]

Page 20/26

## Clinical Investigation Plan (CIP)

- Date and documentation of disposal of devices as per sponsor instructions (if applicable)

## 12 Statements of compliance

The clinical investigation will be conducted in accordance with the ethical principles that have their origin in the Declaration of Helsinki (Declaration of Helsinki, 2018).

The Clinical investigation will be in compliance with the ISO 14155 (ISO\_14155, 2020) and the following national and regional (if applicable) regulations: N/A

The clinical investigation will not begin until the required approval/ favorable opinion from the EC and regulatory authority (if applicable) have been obtained, (To be checked, if appropriate).

Any additional requirements imposed by the EC or regulatory authority will be followed. (To be checked, if appropriate).

- This clinical investigation is covered with the following insurance:  
[REDACTED]  
[REDACTED]
- Professional liability insurance from HPSO
  - [REDACTED]

This investigation is solely financed by Sonova AG and will be conducted internally.

## 13 Informed consent process

### 13.1 Process for obtaining informed consent

At the beginning of the first appointment, investigators will hand the consent form to the participant in a private setting and grant sufficient time to read the whole form. The consent form contains detailed information about incentives and reimbursement. Any questions will be answered and the participant will be given sufficient time to decide whether or not they want to participate in the study. After the participant signed two copies of the consent form, the researcher will sign both copies as well and provide one copy to the participant.

In case of changes to the procedures described in the consent form, the participant will be informed at the beginning of an appointment.

### 13.2 Process for obtaining informed consent in emergency situations

This Chapter is not applicable for this investigation. Informed Consent will only be obtained by investigation participants who can provide informed consent themselves before enrollment.

## 14 Adverse events, adverse device effects and device deficiencies

Device deficiencies and all **adverse events (AE)** including all **serious adverse events (SAE)** are collected, fully investigated and documented in the source document and appropriate case report form (CRF) during the entire investigation period, i.e. from participant's informed consent until the last protocol-specific procedure, including a safety follow-up period (ISO\_14155,

---

SRF-371

Confidential and proprietary.

This document and its contents are confidential and proprietary to Sonova and shall not be reproduced or otherwise disclosed to anyone other than Sonova employees without written authorization from Sonova.

This printout is an uncontrolled copy. The original is stored in the Document Management System  
Template: TPL-368 [2]

## Clinical Investigation Plan (CIP)

2020). Documentation includes dates of event, treatment, resolution, assessment of seriousness and causal relationship to device and/or investigation procedure.

Information on AEs is systematically collected during the regular investigation visits, and phone calls (if applicable).

### 14.1 Definition and Assessment of Adverse Events and other safety related events

#### 14.1.1 Adverse Events (Definition)

An adverse event is an untoward medical occurrence, unintended disease or injury, or untoward clinical signs (including abnormal laboratory findings) in subjects, users or other persons, whether or not related to the investigational medical device (ISO\_14155, 2020)

- Note1: this definition includes events related to the investigational medical device or the comparator.
- Note2: This definition includes events related to the procedures involved.
- Note3: For users or other persons, this definition is restricted to events related to the use of investigational medical device

#### 14.1.2 Serious Adverse Event

A SAE is an AE that led to any of the following

- a) death
- b) serious deterioration in the health of the subject, users or other persons as defined by one or more of the following
  - life-threatening illness or injury, or
  - permanent impairment to a body structure or a body function including chronic diseases, or
  - in-patient hospitalization or prolongation hospitalization, or
  - medical or surgical intervention to prevent life-threatening illness or injury or permanent impairment to a body structure or a body function
- c) foetal distress, foetal death or a congenital abnormality or birth defect

Note: Planned hospitalization for a pre-existing condition, or a procedure required by the Clinical Investigation Plan, without serious deterioration health, is not considered a serious adverse event (ISO\_14155, 2020)

#### 14.1.3 Adverse Device Effect

An adverse device effect, is an adverse event related to the use of an investigational medical device (ISO\_14155, 2020)

- Note: This definition includes AEs resulting from insufficient or inadequate instructions for use, deployment, implantation, installation, or preparation, or any malfunction of the investigational medical device.
- Note: This definition includes any event resulting from use error or from intentional misuse of the investigational medical device

SRF-371

Confidential and proprietary.

This document and its contents are confidential and proprietary to Sonova and shall not be reproduced or otherwise disclosed to anyone other than Sonova employees without written authorization from Sonova.

This printout is an uncontrolled copy. The original is stored in the Document Management System  
Template: TPL-368 [2]

Page 22/26

## Clinical Investigation Plan (CIP)

### 14.1.4 Health hazards

Health hazards are findings in the trial that may affect the safety of investigation participants and, which require preventive or corrective measures intended to protect the health and safety of investigation participants SAE

### 14.1.5 Device Deficiencies (Definition)

A Device Deficiency is an inadequacy of a medical device with respect to its identity, quality, durability, reliability, usability, safety or performance (ISO\_14155, 2020)

- Note: Device deficiency include malfunctions, use errors, and inadequacy in the information supplied by the manufacturer including labelling
- Note: This definition includes device deficiencies related to the investigational medical device or the comparator

### 14.1.6 Causal relationship of SAE

A causal relationship towards the medical device or investigation procedure should be rated as follows:

**Not related:** The relationship to the device or procedures can be excluded.

**Unlikely:** The relationship with the use of the device seems not relevant and/or the event can be reasonably explained by another cause, but additional information may be obtained.

**Possible:** The relationship with the use of the investigational device is weak but cannot be ruled out completely. Alternative causes are also possible.

**Probable:** The relationship with the use of the investigational device seems relevant and/or the event cannot be reasonably explained by another cause.

**Causal relationship:** The serious event is associated with the investigational device or with procedures beyond reasonable doubt.

Device deficiencies that might have led to an SAE are always related to the medical device.

## 14.2 Foreseeable adverse events and anticipated adverse device effect

Table 2: List of foreseeable adverse events and anticipated adverse device effects

Polarion [Risk ID]	Foreseeable AE	Anticipated ADE	Likely incidence	Mitigation or treatment
N/A	Patient Discomfort	N/A	Likeliness is limited	Training
N/A	Tympanic Membrane Perforation	N/A	Unlikely	Training, within scope of practice of researchers
N/A	Skin Sensitivity	N/A	Unlikely	Training to limit time of contact with equipment
N/A	Skin Abrasion and Irritation	N/A	Unlikely	Training, within scope of practice of researchers

SRF-371

Confidential and proprietary.

This document and its contents are confidential and proprietary to Sonova and shall not be reproduced or otherwise disclosed to anyone other than Sonova employees without written authorization from Sonova.

This printout is an uncontrolled copy. The original is stored in the Document Management System  
 Template: TPL-368 [2]

## Clinical Investigation Plan (CIP)

No serious adverse event that could be related to the investigational device or investigation procedures are expected during this clinical investigation.

### 14.3 Non-reportable adverse events

*Table 3: List of all non-reportable AEs including rational*

Non-reportable AEs	Rationale
N/A	The investigation is a one time appointment lasting approximately an hour. An event that happens during this investigation would not be reported if it is deemed unrelated. If an event does occur, it is likely unrelated due to the short timeframe of the investigation.

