### 4.3 Risks associated with participation in the clinical investigation

The investigatory procedure and comparator procedure both carry risks typical to the standard of care of earmold impression procedures. When placing an object in the auditory canal, there is risk of discomfort to the participant. In addition, when equipment is placed too deep into the

SRF-371

Confidential and proprietary.

This document and its contents are confidential and proprietary to Sonova and shall not be reproduced or otherwise disclosed to anyone other than Sonova employees without written authorization from Sonova.

This printout is an uncontrolled copy. The original is stored in the Document Management System  
Template: TPL-368 [2]

Page 10/26

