## Clinical Investigation Plan (CIP)

auditory canal, there is risk for damage or perforation of the tympanic membrane. There are risks of skin sensitivity to material of the devices inserted into the auditory canal, as well as risk for abrasions or irritation while placing these devices during the procedure.

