## Clinical Investigation Plan (CIP)

### 6.2 Investigational device(s) and comparator(s)

Description of the exposure to the investigational device(s)	For each subject, the investigational device (█████ 3D ear scanner) will have an exposure time of approximately 15 minutes, or the length of time it takes to complete a 3D ear scan in its entirety.
Description of the exposure to the comparator(s), if used.	For each subject, the comparator (silicone earmold impression procedure) will occur for approximately 15 minutes, or the length of time it takes to complete a traditional silicone earmold impression.
List of any other medical device to be used during the clinical investigation (if applicable)	N/A
Number of investigational devices to be used, and justification	1 – The investigational device can be reused and sanitized between subjects in accordance with the manufacturer recommendations.

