## Clinical Investigation Plan (CIP)

Expected duration of each participant's participation	Approximately 30 minutes
Number of participants required to be included in the clinical investigation, and where needed anticipated distribution of enrolment among the participating clinical sites.	30 subjects seen at PARC
Estimated time needed to select this number (i.e. enrolment period).	Approximately 2 weeks
Relationship of investigation population to target population	Investigation population will contain a variety of external auditory canal sizes and shapes, relatable to the average patient without any external auditory canal anomalies.
Information on vulnerable, pregnant and breastfeeding population, if applicable.	N/A

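### Section 14.3 presumes that any adverse event is unrelated because the visit is short, and its reporting exemption contradicts Table 4 and section 14.4.2 for serious events

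*Combined protocol and SAP*

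**What the plan says.** The rationale cell of Table 3 in section 14.3 makes three statements in sequence. On duration: "The investigation is a one time appointment lasting approximately an hour". On reporting: "An event that happens during this investigation would not be reported if it is deemed unrelated". On causality: "If an event does occur, it is likely unrelated due to the short timeframe of the investigation". The neighbouring cell, which should list the non-reportable events, reads N/A.

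Section 4.3 describes the risks of both procedures. It says "When placing an object in the auditory canal, there is risk of discomfort to the participant", and of equipment placed too deep it says "there is risk for damage or perforation of the tympanic membrane". It adds skin sensitivity to the inserted materials, and abrasion or irritation from placing them. Table 2 in section 14.2 lists the same events as foreseeable, with operator training as mitigation.

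Table 4 in section 14.4.1 gives times for the principal investigator's reports. Adverse events, serious adverse events, health hazards and device deficiencies all go to the Investigation Manager in 1-2 days and to the Ethics Commission in 5 days. Section 14.4.2 sends serious adverse events to the FDA.

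**The concern.** Closeness in time to a procedure is ordinarily evidence for a causal link. Section 14.3 treats it as evidence against one, and does so next to a rule under which the causality judgement decides whether an event is reported. A procedure-related event could be judged unrelated on the strength of that sentence and then not be sent on. Because the exemption is not confined to non-serious events, its wording also reaches serious ones, and staff would face two conflicting instructions. At stake is safety reporting only. The comparison of procedure times does not depend on it.

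**Working it through.** The plan gives no event rates, only verbal likelihoods such as unlikely, so there is no figure to reproduce and no expected count to compute. The check compares the texts.

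**1. Direction of the argument.** Let π be the probability that the procedures cause an event, λ the background rate of unrelated events, and T the length of the visit. For rare events, the share of observed events that are procedure-related is about π / (π + λT).
- If π comes from inserting objects in the ear and does not depend on T, shortening the visit lowers λT and raises the share.
- If π is itself proportional to T, the share does not change.

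In neither case does a short visit make an observed event less likely to be related. A short visit makes any event less likely to occur, which is a different claim. Table 1 in section 4.5 makes that valid claim when it argues that limited contact time reduces skin sensitivity. Section 14.3 turns it into a claim about causality.

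**2. Presumption against the plan's own risk list.**

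| Table 2 foreseeable event | Source given in section 4.3 |
|---|---|
| Discomfort | Object placed in the canal |
| Tympanic membrane perforation | Equipment placed too deep |
| Skin sensitivity | Material of the inserted devices |
| Abrasion and irritation | Placing the devices |

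All 4 of 4 are tied to the study procedures. Table 2 shows N/A under anticipated device effects, but this does not remove the conflict: Note 2 to the definition in section 14.1.1 counts procedure-related events as adverse events.

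**3. Exemption against the reporting rules.**

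| Text | Relatedness condition | Seriousness limit or separate rule |
|---|---|---|
| 14.3, rationale cell | Yes: unrelated events are not reported | None |
| 14.3, list cell | N/A, no event listed | N/A |
| Table 4, four rows | 0 of 4 | Separate row for serious events |
| 14.4.2, FDA report | None | Applies to serious events |

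A section on non-reportable events may carve exceptions out of Table 4, so for non-serious events the exemption is not in itself an error. For a serious event judged unrelated, section 14.3 says not to report while Table 4 and section 14.4.2 say to report. The N/A in the list cell adds a contradiction inside Table 3: nothing is listed as exempt, yet the next cell states a general exemption.

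**4. What still happens to a misjudged event.**
- Section 14 has every event investigated and documented, with seriousness and causal relationship assessed.
- Section 14.4.2 has the investigation manager contact the principal investigator within 24 hours of any adverse event, to settle reporting and evaluate the relationship.
- Section 6.3 pauses the study until the event is reviewed.

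Of the two active recipients in Table 4 (the Competent Authority column is N/A), the Investigation Manager is thus involved in any case. The report mainly exposed is the 5-day one to the Ethics Commission.

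**The case against.** The strongest reply is that relatedness is not left to a presumption. Section 14.4.2 names the two roles who evaluate it, so the sentence in section 14.3 is a stated expectation and not a classification rule. A missed report would need both roles to misjudge the same event. This stands, and it is why the point is minor. It does not rescue the sentence, which gives those two roles a wrong reason to lean towards unrelated.

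A reader might infer that the plan exempts serious events from reporting. The documents do not support that. Table 4 has a specific row for serious events and section 14.4.2 has a specific FDA rule, so the plan contradicts itself and does not clearly exempt them. Nor can one infer that events would go unrecorded or unassessed: section 14.3 touches reporting only.

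It is also tempting to argue from visit time. Section 6.2 gives about 15 minutes to each procedure, and section 6.3 gives participation as "Approximately 30 minutes", as if the two procedures filled the visit. That inference fails. Section 6.4.1 adds real-ear measurements, tympanometry, reflex thresholds and questionnaires, and section 13.1 adds consent. In any case, share of time does not measure probability of causation. The difference between the durations in sections 6.3 and 14.3 is a separate inconsistency.

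**Conclusion.** The point holds: section 14.3 is wrong as written, and severity is minor. The causal presumption is unsound and conflicts with the plan's own account of all four foreseeable events. The exemption contradicts the reporting rules where an event is serious. The practical consequence is limited mainly to a late or missing Ethics Commission report for a procedure-related event misjudged as unrelated, in a study of 30 participants seen once. The conclusion assumes that the safeguards in sections 6.3, 14 and 14.4.2 operate as written. How often such a misjudgement would occur cannot be estimated from the documents.

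**What to change.** Delete the sentence in section 14.3 that presumes events to be unrelated. Then choose one of two options:

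1. Delete the exemption, so that Table 4 governs all reporting.
2. Keep a restricted exemption. It would cover only events that are non-serious, are not among the four in Table 2, and are rated Not related in the section 14.4.2 evaluation. The exclusion of Table 2 events has to be explicit. Without it, non-serious discomfort or irritation rated Not related would still go unreported.

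Under either option, state that all serious events follow section 14.4, and make the list cell of Table 3 agree with the rule adopted. Case-by-case evaluation and the 1-2 day report to the Investigation Manager are already in the plan and need no new text.

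The cost is a short wording amendment and a few extra reports at most. Procedures, sample size and the primary time analysis do not change.
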